1 PROTOCOL SUMMARY

1.1 SYNOPSIS	
Title:	A Single Arm Study of Resting State Functional Magnetic Resonance Imaging (rs- fMRI)-Guided Theta Burst Stimulation (TBS) in Early-Stage Alzheimer's Disease (AD)
IRB Number:	
Study Description: Objectives:	Alzheimer's disease (AD) is a progressive neurodegenerative condition affecting 6.2 million individuals in the United States, resulting in an annual cost of care of \$305 billion. AD is functionally characterized by progressive degeneration of large-scale brain networks (LSBNs), including the default mode network (DMN) presumably from the deposition of amyloid plaques and neurofibrillary tangles. Available FDA-approved medications for AD such as donepezil and memantine offer limited benefit and modest impact on quality of life. In combination with resting state functional MRI (rs-fMRI), transcranial magnetic stimulation (TMS) with intermittent theta burst stimulation (iTBS) offers a non-invasive alternative to pharmacotherapy in persons with AD. We propose a pilot trial using rs-fMRI to target dysfunctional LSBNs in early stage AD. Primary Aim : To estimate the effect of rs-fMRI-guided TBS on connectivity dysfunction within the temporal area G dorsal (TGd) in persons with early stage AD.
	Exploratory Aim 1: To estimate the effect of rs-fMRI-guided TBS on the Repeatable Battery for the Assessment of Neuropsychological Status (RBANS) score in persons with early stage AD.
	Exploratory Aim 2: To estimate the effect of rs-fMRI-guided TBS on the Geriatric Depression Score (GDS) in persons with early stage AD.
	Exploratory Aim 3: To identify and estimate the effect of rs-fMRI-guided TBS on two additional dysfunctional parcellations within the default modal network (DMN), central executive network (CEN), and salience network (SN) in persons with early stage AD.
Endpoints:	 Primary Endpoint: Connectivity Measures of the TGd parcellations at baseline and post-treatment Exploratory Endpoints: RBANS at baseline and post-treatment GDS at baseline and post-treatment Connectivity levels of other parcellations that are anomalous
 Connectivity levels of other parcellations that are anomalous Study Population: The study will enroll 10 subjects with a diagnosis of early stage AD (mild cognitive impairment or mild AD). Inclusion criteria: Established diagnosis of MCI/mild AD Evidence for CNS amyloidosis (e.g., Amyloid PET or CSF biomarkers consistent with AD) Prior brain imaging performed MMSE >24 CDR 0.5-1 	

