	Stable dose of cholinesterase inhibitors and memantine for at least one month			
	7. Subjects are between 40-90 years of age			
	Exclusion Criteria:			
	 Non-AD dementia including, but not limited to, Lewy body dementia, frontotemporal dementia, vascular dementia, Jakob-Creutzfeldt disease, etc. 			
	2. Inability to tolerate rs-fMRI			
	3. Contraindication of rs-fMRI due to implants or metal			
	4. Seizure disorder			
	5. Alcoholism			
Description of Sites/Facilities	Participants will be enrolled at HealthPartners Neuroscience Center,			
Enrolling	located at [name].			
Participants:				
Description of	All subjects will receive treatment with intermittent theta burst stimulation			
Study	(iTBS), There will be a total of 5 iTBS sessions per treatment visit, and a total of			
Intervention:	5 treatment visits distributed over a two-week period (#3 during week 1 and #2 during week 2). All patients will receive iTBS to the right TGd region. In addition, we will further provide TBS treatment for two additional sites within the LSBNs that is found to contain the greatest number of connectivity anomalies. Data from the Infinitome program will be exported to the Localite TMS Navigator; the navigator is a device that visualizes brain regions to facilitate correct positioning of patient and coil based on the coordinates from the Infinitome			
Study Duration:	the Infinitome analysis.			
Study Duration.	The duration of this study is 1.5 years.			
Participant Duration:	10-12 weeks			

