4 STUDY DESIGN

4.1 OVERALL DESIGN

This investigation is a prospective single arm treatment trial in early stage AD (MCI and mild AD).

Primary Aim

To estimate the effect of rs-fMRI-guided TBS on connectivity dysfunction within the temporal area temporal area G dorsal (TGd) in persons with early stage AD.

Exploratory Aims

- 1. To estimate the effect of rs-fMRI-guided TBS on the Repeatable Battery for the Assessment of Neuropsychological Status (RBANS) score in persons with early stage AD.
- 2. To estimate the effect of rs-fMRI-guided TBS on the Geriatric Depression Score (GDS) in persons with early stage AD.
- **3.** To identify and estimate the effect of rs-fMRI-guided TBS on two additional dysfunctional parcellations within the default modal network (DMN), central executive network (CEN), and salience network (SN) in persons with early stage AD.

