6.2 MEASURES TO MINIMIZE BIAS: RANDOMIZATION AND BLINDING

N/A

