8.2.7 CONNECTOMIC ANALYSIS

All subject images will be processed using the infinitome tool. This will be used to conduct a connectomic analysis to identify large scale brain networks.

The Infinitome tool creates a machine learning-based, subject specific version of the Human Connectome Project-Multimodal Parcellation (HCP-MMP1) atlas based upon diffusion tractography structural connectivity (Figure 3). All data uploaded to the cloud is de-identified. This novel method was created by training a machine learning model on 200 normal subjects by first processing T1 and DT images. An HCP-MMP1 atlas in NIFTI MNI space is then warped onto

each brain and the structural connectivity calculated between every pair of this atlas and a set of ROI containing 8 subcortical structures per hemisphere and the brainstem based on the streamlines which terminated within an ROI. To ensure this atlas is applicable to pathologically distorted brains, a machine-learning tool takes the individual's DTI or CSD tractography and locates every voxel and reassigns them to an area that fits more accurately with the structural connection to create a personalized adjusted atlas. The personalized patient atlas is used to subset the resting-state and CSD tractography data to create Structural and Functional connectivity matrices. When these matrices are compared to other individuals using machinelearning, an output of structural and functional anomaly matrices demonstrates the abnormal connectivity in this subject's brain (Figure 4). Abnormal connectivity is determined as a 3-sigma outlier for that correlation, after excluding the highest variance 1/3 of pairs, to further reduce the false discovery rate. Assignment of parcellations to various large-scale brain networks is based on several previous coordinate based meta-analysis and matching the HCP-MMP1 parcellations to the coordinates of the ALE in MNI space, which has been previously published (or in review presently) by our group.

Figure 4: Connectomic Analysis

[figure not shown]
[figure not shown]

Figure 3: Anomaly Matrix for LSBNs in Temporal Lobe

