9 STATISTICAL CONSIDERATIONS

9.1.1 STATSTICAL PLAN OVERVIEW

The study population demographics (age, race, etc.) will be described using appropriate summary measures (i.e. means, standard deviations, or medians for continuous variables and counts or percentages for discrete variables). Disease characteristics (MMSE and CDR) will also be summarized to describe our population.

The primary aim will be assessed by calculating the difference and corresponding 95% confidence interval between follow-up and baseline connectivity measures of the TGd parcellations. We will conduct a t-test to statistically test if that difference is greater than 0, which would indicate a non-null effect of the TBS intervention on those areas of the brain.

Exploratory aims 1 and 2 will be analyzed similarly to the primary aim.

For exploratory aim 3, parcellations within the DMN, CEN, or SN associated with \geq 4 anomalies on the baseline matrix will be considered for the third TBS treatment. We will descriptively note whether there are shared anomalous parcellations between study patients. If one area of the

brain is anomalous in at least half of the subjects, we will target that area with the third TBS treatment for all patients and analyze it similarly the primary aim. If no such area rises to this level, we will simply describe changes from baseline for the individual areas treated for each patient.

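### Section 9.1.1 reads a positive pre-post t-test on TGd connectivity as a TBS effect, but a single-arm comparison of two scans can show only a change from baseline

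*Combined protocol and SAP*

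**What the plan says.** Section 4.1 declares the design openly: "This investigation is a prospective single arm treatment trial in early stage AD (MCI and mild AD"). Section 6.2, headed "MEASURES TO MINIMIZE BIAS: RANDOMIZATION AND BLINDING", contains only N/A. The Synopsis adds that "All patients will receive iTBS to the right TGd region".

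MRI is done at baseline (Visit 2, Week 1) and once more at Visit 8 (Week 10, six weeks after the last treatment), per Table 1 and Section 8.1.4.

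For the primary aim, Section 9.1.1 specifies "calculating the difference and corresponding 95% confidence interval between follow-up and baseline connectivity measures of the TGd parcellations". It continues: "We will conduct a t-test to statistically test if that difference is greater than 0", and gives the meaning of a positive result: "which would indicate a non-null effect of the TBS intervention on those areas of the brain". Exploratory aims 1 and 2 (RBANS, GDS) follow the same approach. No section qualifies this attribution, and none states what change would be expected without treatment.

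**The concern.** The null hypothesis tested is that the mean change from baseline is zero. The conclusion drawn concerns a different hypothesis, that the TBS effect is zero. The two coincide only if connectivity would stay constant, on average, over about nine weeks without stimulation.

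The protocol does not claim this, and its own background points away from it: "AD is functionally characterized by progressive degeneration of large-scale brain networks (LSBNs), including the default mode network (DMN"). Systematic differences between scanning sessions, such as scanner drift, head motion or arousal, are another possible source of non-TBS change, although the documents do not quantify them.

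The clause sets in advance how the primary result will be read. Section 2.2.2 says the work will support a future grant application, and Table 2 says the exploratory endpoints provide pilot data for larger trials. A claim of effect that the design cannot support would carry over into that use.

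**Working it through.** **Inputs.** From Section 9.1.2: n = 10; SD 0.033; meaningful change 0.033, so d = 0.033/0.033 = 1; stated power 80%. From Section 9.1.1: a t-test on the within-patient difference with a 95% CI. Alpha and sidedness are not stated. The CI suggests two-sided 0.05, while the wording about exceeding zero could mean one-sided, so both are shown.

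**Formula.** Paired t-test, df = 9, noncentrality = d × √10. Critical values are 2.262 (two-sided 0.05) and 1.833 (one-sided 0.05).

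**Step 1: the plan's own figure.** With d = 1 the noncentrality is 3.162. Two-sided power is 80.3%, which reproduces the stated 80%; one-sided 0.05 gives 89.8%. The stated power therefore matches a two-sided test and treats 0.033 as the SD of the within-patient change. The arithmetic is not at fault.

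**Step 2: no TBS effect, systematic non-TBS shift.** Here d is the shift divided by the SD of the change. Entries are the probability of a significant *increase*.

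| Shift (SD of change) | Shift if SD = 0.033 | Upward, two-sided 0.05 | Upward, one-sided 0.05 | Downward, two-sided 0.05 | Downward, one-sided 0.05 |
|---|---|---|---|---|---|
| 0 | 0 | 2.5% | 5.0% | 2.5% | 5.0% |
| 0.25 | 0.008 | 10.6% | 18.1% | 0.4% | 0.9% |
| 0.50 | 0.017 | 29.3% | 42.7% | 0.03% | 0.09% |
| 0.75 | 0.025 | 56.2% | 70.7% | <0.01% | <0.01% |
| 1.00 | 0.033 | 80.3% | 89.8% | <0.01% | <0.01% |

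An upward shift of 1 SD produces a positive result as often as a true TBS effect of the design size does. The test cannot tell them apart.

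**Step 3: masking.** If the true TBS effect is 1 SD and the non-TBS shift is downward by 0.25, 0.5 or 0.75 SD, the net d is 0.75, 0.5 or 0.25. Two-sided power falls from 80% to 56%, 29% or 11%.

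**Step 4: what the existing scans could add.** Section 8.2.7 says each patient's personalised atlas is "used to subset the resting-state and CSD tractography data to create Structural and Functional connectivity matrices". Only three targets are stimulated (Section 6.1.2), so unstimulated parcellations are available at both visits. The HCP reference sample is not described as rescanned, so standardising against it does not remove change over time.

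For the contrast TGd change minus control-region change, with equal SDs and correlation r between the two changes, SD = 0.033 × √(2(1 − r)):

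| r | SD of contrast | Power for 0.033, n = 10, two-sided |
|---|---|---|
| 0 | 0.0467 | 51% |
| 0.25 | 0.0404 | 63% |
| 0.5 | 0.0330 | 80% |
| 0.75 | 0.0233 | 98% |

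In simulation with drift fully shared by both sets of regions (r = 0.5), the false-positive rate of the contrast was 4.9% to 5.1%. That result depends on the drift being shared. The equal SDs and the values of r are assumptions.

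**The case against.** The strongest reply is that this is an openly declared single-arm pilot whose aim is to estimate, with a 95% CI, and that nobody would mistake it for a controlled trial. That is fair to the design, which is not criticised here. It does not answer the clause in Section 9.1.1, which draws a causal conclusion with no caveat elsewhere.

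Several further objections stand and limit the point:

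- A reader might infer from the 11% to 56% range that the planned test has an inflated error rate in this trial. The documents do not support that. The range needs a *systematic upward* shift. Random session noise averages out, and the one documented mechanism, progressive degeneration, would make a false increase rarer if it lowers connectivity (Step 2, downward columns).
- A reader might infer that a significant result would trigger a larger trial. There is no go/no-go rule tied to the p-value.
- Some non-treatment causes are partly addressed: Section 8.2.4.1 notes alternate RBANS forms against practice effects, and Section 5.1 requires stable dosing of cholinesterase inhibitors and memantine for at least one month at entry.
- A reader might infer that a contrast with untreated regions would restore attribution to TBS. It would not. It removes only drift common to both sets of regions. Section 2.1 places TGd in the DMN, so controls outside the DMN leave DMN-specific change in place. Spread of stimulation could bias the contrast either way, and precision may fall (Step 4). It also does nothing for RBANS or GDS.

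**Conclusion.** The interpretation rule for the primary endpoint is wrong as written. A positive test would show that mean TGd connectivity rose between two dates; it would not show that TBS caused the rise. The same holds for RBANS and GDS.

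The possible error runs in both directions. With no TBS effect, systematic upward shifts of 0.25 to 0.75 SD of the change give a significant increase in about 11% to 56% of trials (two-sided 0.05) or 18% to 71% (one-sided 0.05). Downward shifts of the same size would tend to mask a real effect. These figures assume n = 10 with complete data, normally distributed changes and, where shown on the connectivity scale, an SD of change of 0.033. The documents give no test-retest or untreated-change data, so the figures illustrate what is possible and do not estimate bias in this trial.

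The conclusion concerns the stated inference. The single-arm design, the estimate, the confidence interval and the power calculation's arithmetic are not faulted here.

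**What to change.** **Needed, in Section 9.1.1:**

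1. Replace the causal clause with: a difference from 0 indicates a change from baseline; without a control group it cannot be attributed to TBS.
2. Apply the same wording to RBANS and GDS.
3. State the sidedness and alpha of the t-test. The stated 80% power matches two-sided 0.05.

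This is a text change only, with no effect on patients, visits, scans or sample size.

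**Optional, supportive:** from the matrices already produced, compute for each patient the TGd change minus the mean change over a list of unstimulated parcellations, leaving out edges to the stimulated targets. Fix the list before any follow-up scan is analysed. Report the mean and 95% CI beside the primary result. State with it that it removes only drift common to both sets of regions, does not remove DMN-specific change if the controls lie outside the DMN, may be biased in either direction by spread of stimulation, may be less precise than the primary estimate, and does not establish a TBS effect. The cost is one additional computation on existing data.

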6.1.2 DOSING AND ADMINISTRATION

There will be a total of 25 intermittent theta burst sessions (iTBS) spread evenly across 5 treatment visits (5 sessions per treatment visit), all distributed over a two-week period (#3 treatment visits during week 1 and #2 during week 2). Intermittent theta burst sessions will be administered at the following settings, which have been used in a standardized manner by our collaborators in their TMS clinic:

Table 3: TMS Treatment Parameters

Resting Motor Threshold	80%	
# of Pulses/Session	1200 pulses (40 cycles x 10 burst pulses x 3	
	pulses per burst pulse)	
Inter-Train Interval	8 sec	
Pulse Frequency in Burst	50 Hz	
Session Length	15-30 min	
Time between Sessions	45 min to Hour	
Number of Targets	3	
Number of Sessions per Day	5	
Treatment Days	5	
Total Pulses per Day	18,000	
Total Pulses for Treatment	90,000	

The treatment regime above will be applied to a total of three regions of interest or parcellations (right TGd + two other sites found to have greatest # of anomalies). The interval between treatment of separate regions of interest (target) will be 2 minutes. The interval between iTBS sessions within the same treatment visit will be 45-60 minutes. Details of the operations of TMS and intervention will be included in a SOP or User guide that will be kept on site.

During the treatment, the TMS operator will be in the room and trained to activate the seizure protocol

(https://healthpartnersconnect.sharepoint.com/:b:/r/sites/bhc/TMS%20Library/Safety/Emergency%20Management%2 0of%20Seizures%20Standing%20Order.pdf?csf=1&web=1&e=p5h4Gg. All patients will be screened with the TASS screening questions. Vital signs will be monitored prior to and after treatment in participants.

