8.1.2 BASELINE VISIT (VISIT 2) -WEEK 1 (± 7 DAYS)

- Verify inclusion/exclusion criteria
- Neuropsychological battery as mentioned in Section 8.2.
- This visit is at the clinic (HealthPartners Neuroscience Center [NSC]), is about 2 hours. This may be extended depending on availability of Imaging slot.

- Subject will undergo MRI imaging as mentioned in section 8.2
- Subject will be screened for TMS safety
- Review concomitant medications
- Record any adverse or serious adverse events

8.1.3 TREATMENT VISIT (VISTS 3-5 AND VISITS 6,7) (5 DAYS OVER 2 WEEKS, ± 7 DAYS AFTER VISIT 2)

- Verify inclusion/exclusion criteria
- Motor threshold mapping in Visit 3. Visit 3 will be 5 -7 hours. Visits 4-7 will be 4-6 hours each.
- All visits will be at NSC
- Subject will receive 5 theta burst stimulation sessions at each of the treatment visits
- Visits will be on alternating days (weekdays)
- Review concomitant medications at each visit
- Record any adverse or serious adverse events at each visit

8.1.4 FOLLOW-UP/REPEAT VISIT (VISIT 8)(WEEK 10, 6 WEEKS AFTER VISIT 7 ± 7 DAYS)

- Verify inclusion/exclusion criteria
- Neuropsychological battery as mentioned in Section 8.2.
- This visit is at the clinic (HealthPartners Neuroscience Center [NSC]), is about 2 hours. This may be extended depending on availability of Imaging slot.
- Subject will undergo MRI imaging as mentioned in section 8.2
- Review concomitant medications
- Record any adverse or serious adverse events

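### Exploratory aim 3 measures change from the same scan that picked its sites, so part of any move toward normal can be regression to the mean, and section 9.1.1 has no caveat (minor)

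*Combined protocol and SAP*

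**What the plan says.** **How the sites are chosen.** Right TGd is stimulated in every patient. The synopsis (1.1) adds "two additional sites within the LSBNs that is found to contain the greatest number of connectivity anomalies", and section 6.1.2 gives the targets as "right TGd + two other sites found to have greatest # of anomalies". Section 8.2.7 defines an anomaly: "Abnormal connectivity is determined as a 3-sigma outlier for that correlation, after excluding the highest variance 1/3 of pairs". Section 9.1.1 sets a threshold for one of the extra sites: parcellations in the three named networks with at least "4 anomalies on the baseline matrix will be considered for the third TBS treatment".

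**When scans are taken.** The schedule of activities has MRI at Visit 2 (baseline) and Visit 8 (week 10) only. Sections 8.1.2 and 8.1.4 carry the same line: "Subject will undergo MRI imaging as mentioned in section 8.2". Section 4.1 describes a single-arm trial, and section 6.2 on measures against bias is marked not applicable.

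**How aim 3 is analysed.** When half or more of the patients share an anomalous area, the instruction is: "we will target that area with the third TBS treatment for all patients and analyze it similarly the primary aim". For the primary aim, the t-test asks whether the difference exceeds zero, "which would indicate a non-null effect of the TBS intervention on those areas of the brain". If no area is shared that widely, "we will simply describe changes from baseline for the individual areas treated for each patient". Section 9.1.1 speaks only of the third treatment. It states no analysis for the other extra site when an area is shared.

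**The concern.** The baseline scan does two jobs in aim 3: it selects the sites and it is the starting point for their change. A site chosen for having many extreme readings is chosen partly for that day's measurement error. On rescanning, the error is drawn afresh and the readings tend to move back, with or without stimulation. Leaving out the highest-variance third of pairs reduces false anomalies but does not separate selection from baseline measurement. There is no second pre-treatment scan, control arm or planned comparison with untreated areas that would reveal the drift.

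Aim 3 is framed as estimating the effect of TBS on these sites, and section 3 justifies the exploratory endpoints as pilot data for larger trials. A pre-post shift labelled as an effect could be carried into the planning of the next study.

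**Working it through.** **1. The plan's own figure.** Section 9.1.2 gives n = 10, a change of 0.033 and an SD of 0.033, so d = 1. For a paired t-test with 9 df, noncentrality √10 = 3.16 and two-sided 0.05 (implied by the 95% CI), power is 80.3%. This matches the stated 80%, but it concerns right TGd. The documents give no figure for aim 3.

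**2. Mechanism for one link.** Let r be the scan-rescan correlation, which the documents do not give; 0.5, 0.7 and 0.9 are assumed throughout. On the scale of the normal reference, with patient spread 1.0:

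- E[z | z > 3] = φ(3) / (1 − Φ(3)) = 3.283.
- Expected drift with no treatment = (1 − r) × 3.283 = 1.64, 0.98, 0.33 SD.
- With a persistent disease shift m, drift = (1 − r) × (E − m). For m = 1, E = 3.373 and drift is 1.19, 0.71, 0.24. For m = 2, E = 3.525 and drift is 0.76, 0.46, 0.15.

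These are single-link values, not the plan's outcome. Section 9.1.2 points to an average over an area's links, so the rest uses a signed average.

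**3. Averaged measure, by hand.** Section 2.1 gives 379 areas, hence 378 links per area. Dropping a third leaves about 252. Take a site with exactly 4 anomalies, all in one direction, independent links and spread 1.0. The other 248 links average φ(3)/Φ(3) = 0.0044 the other way.

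- Baseline mean = (4 × 3.283 − 248 × 0.0044) / 252 = 0.048.
- Between-patient SD of that mean = 1/√252 = 0.063.
- Ratio = 0.76, so drift = (1 − r) × 0.76 = 0.38, 0.23, 0.08 between-patient SD.
- With two high and two low anomalies the terms cancel and drift is about zero.

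If 20% of link variance is shared within a parcellation (assumed), simulation with the at-least-4 rule gives about 1.2 SD at r = 0.5.

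**4. Shared-area branch, simulated with no treatment effect.** Assumed: patient spread 1.3 (at which a shared area nearly always exists), 60 candidate parcellations including right TGd, 252 links each, no persistent disease shift, 10 patients and 600 trials per setting. The shared area is the one with at least 4 anomalies in the most patients, and in at least 5 of 10. Ranges run over r; drift is in between-patient SD.

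| | Balanced | One direction, independent links | One direction, 20% shared variance |
|---|---|---|---|
| Shared area, drift | about 0 | 0.01-0.09 | 0.06-0.26 |
| Shared area, two-sided rejection | 3.0-5.2% | 3.0-5.2% | 10.5, 7.2, 6.7% (r = 0.5, 0.7, 0.9) |
| Other extra site, drift | about 0 | 0.07-0.34 | 0.22-1.07 |

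The 3.0-5.2% range covers both columns. Simulation error is about 0.9 points at 5% and 1.3 at 10%.

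**5. Cross-check of the rejection rates.** The change has SD √(2(1 − r)) in between-patient SD. At r = 0.5 this is 1, so a drift of 0.26 gives noncentrality 0.26 × √10 = 0.82 and 11.4% rejection; a drift of 0.09 gives 0.28 and 5.8%. At r = 0.9, 0.06/√0.2 = 0.134 gives 0.42 and 6.7%. These agree with the table within simulation error.

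The shared area drifts less because it is tested in all 10 patients, including those in whom it was not anomalous. The other extra site is picked patient by patient.

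**The case against.** The case for leaving the plan alone has real weight. Aim 3 is exploratory, in a 10-patient pilot. The fallback branch is descriptive and already speaks of changes from baseline. The only branch with a test is close to nominal unless anomalies run one way and links share variance, and that 20% is assumed. The simulation gives no area a persistent disease shift, which would reduce the drift, and it drops a third of the pairs at random rather than those with the highest variance. The sentence that reads a difference as an effect is written about TGd; its extension to the shared area rests on the instruction to analyse that area in a similar way.

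All of this limits the size and makes the point minor. It does not remove it. Anomaly direction and reliability are not given, so the plan cannot show that the benign case applies. The objectives call the aim 3 result an effect in both branches, and no section warns otherwise.

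Three stronger readings are tempting, and the documents do not support them.

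- *The primary analysis is biased in the same way.* Right TGd is fixed in advance for every patient, and no eligibility criterion requires a TGd anomaly, so its baseline is not selected.
- *The aim 3 test has badly inflated error.* The table shows otherwise.
- *The large single-link drifts describe the aim 3 result.* The endpoint is connectivity level, and section 9.1.2 points to an average, on which most of that drift is diluted or cancels.

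**Conclusion.** The point holds for exploratory aim 3 only, and it is minor. The overlap between selection and baseline follows directly from the documents; the size does not. It depends on scan-rescan reliability, the direction of the anomalies, shared variance, any persistent disease shift and patient spread, none of which is given.

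Under the assumptions above, artefactual drift on an averaged signed measure runs from about zero (balanced anomalies) to about 0.26 between-patient SD for a shared area. For sites picked per patient it reaches about 1 SD, or about 1.2 under the at-least-4 rule at spread 1.0 and r = 0.5. For orientation, section 9.1.2 treats a change of one SD at right TGd as meaningful, so drift at individually picked sites could, at worst, be of that order. The primary right-TGd analysis and its 80% power figure stand.

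**What to change.** Add two sentences to section 9.1.1, covering both extra sites and both branches:

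1. Results for the aim 3 parcellations are reported as change from baseline. Because these sites were selected on the baseline scan, such change is not by itself evidence of a TBS effect.
2. If a shared area is tested, the primary aim's interpretation of a difference as a treatment effect does not apply to it.

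The wording should name both extra sites, since 9.1.1 now speaks only of the third treatment while sections 1.1 and 6.1.2 describe two; those passages should be reconciled. The change needs no new scans, patients or analyses, and it leaves stimulation and scheduling as they are. Its cost is that aim 3 claims less.

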3 OBJECTIVES AND ENDPOINTS

OBJECTIVES	ENDPOINTS	JUSTIFICATION FOR ENDPOINTS
Primary		
To estimate the effect of rs-fMRI- guided TBS on connectivity dysfunction within the temporal area temporal area G dorsal (TGd) in persons with early stage AD.	Connectivity measures of the TGd parcellations at baseline and post- treatment	Infinitome processed rs- fMRI data that is targeted with TMS
Exploratory		
 To estimate the effect of rs- fMRI-guided TBS on the Repeatable Battery for the Assessment of Neuropsychological Status (RBANS) score in persons with early stage AD. To estimate the effect of rs- fMRI-guided TBS on the Geriatric Depression Score (GDS) in persons with early 	 RBANS at baseline and post- treatment GDS at baseline and post- treatment 	Provide pilot data for larger trials.

Table 2: Objectives and Endpoints

OBJECTIVES	ENDPOINTS	JUSTIFICATION FOR ENDPOINTS
3. To identify and estimate the effect of rs-fMRI-guided TBS on two additional dysfunctional parcellations within the default modal network (DMN), central executive network (CEN), and salience network (SN) in persons with early stage AD.	3. Connectivity levels of other parcellations that are anomalous	

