5 STUDY POPULATION

The study will enroll 10 subjects with a diagnosis of early stage AD (mild cognitive impairment or mild AD). Those patients where fMRI is contraindicated (e.g. implantable device, pacemaker, metallic implants, etc.) or who are unable to tolerate sitting for a one-hour fMRI will be excluded from the study.

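### The shared third target in Section 9.1.1 cannot be assigned to all patients unless five anomalous baseline scans precede the first treatment, and Sections 1.1 and 6.1.2 do not mention it

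*Combined protocol and SAP*

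**What the plan says.** Section 5: "The study will enroll 10 subjects with a diagnosis of early stage AD".

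Section 9.1.1, exploratory aim 3: DMN, CEN or SN parcellations with four or more anomalies on the baseline matrix "will be considered for the third TBS treatment". If one area of the "brain is anomalous in at least half of the subjects", then "we will target that area with the third TBS treatment for all patients and analyze it similarly the primary aim". If no area reaches that level, the plan will only "describe changes from baseline for the individual areas treated for each patient".

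Section 6.1.2: the regimen "will be applied to a total of three regions of interest or parcellations", namely "right TGd + two other sites found to have greatest # of anomalies". The Study Intervention entry of the synopsis (1.1) likewise picks both extra sites by anomaly count. Neither section mentions a shared area or refers to 9.1.1.

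Timing: Section 1.3 puts the baseline scan in Week 1 and treatment in Weeks 2 to 4. Section 8.1.3 dates the treatment visits from the patient's own Visit 2. Neither makes one patient's treatment wait for another patient's scan.

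**The concern.** The rule in 9.1.1 decides where patients are stimulated, and it depends on other patients' scans. The visit schedule runs patient by patient. If entry is staggered, early patients are treated before the shared area can be known. Their third target comes from their own matrix, while later patients' third target comes from the shared-area rule, so the target depends on order of entry.

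Every patient is scanned twice, so change in the shared area can be computed for all 10. In a patient not stimulated there, that change does not estimate the effect of stimulating the area, which is what exploratory aim 3 asks. Averaging the two kinds of patient in one t-test would blur the answer.

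Separately, a TMS operator following 6.1.2 and an analyst following 9.1.1 could name different third targets for the same patient.

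**Working it through.** **The plan's own figure.** The plan gives no number for this rule. Its only calculated figure is the 80% power in 9.1.2, which is for right TGd. It reproduces: n = 10, standardised change 0.033/0.033 = 1, noncentral t with 9 degrees of freedom, and two-sided 5% (assumed, since alpha and sidedness are not stated) give 80.3%. This point does not touch it.

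**When the rule can be decided.** Inputs: 10 subjects (Section 5); half or more (9.1.1).
- Needed: 10/2 = 5 anomalous matrices for the same area, so the trigger comes at the fifth baseline scan at the earliest.
- An area is ruled out once 6 matrices are not anomalous for it, so at the sixth scan at the earliest.
- If the trigger comes at scan k, up to k − 1 patients may have started treatment: up to 4 at k = 5, up to 9 at k = 10.

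**How many have started by the fifth scan.** Accrual is not stated, so this is a range under assumptions: ten evenly spaced baselines over a span S, gap g = S/9, fifth baseline at 4g, and a lag L of 1 to 4 weeks from a patient's scan to first treatment (from 1.3 and its windows). Patient i (i = 0 to 3) has started if i × g + L < 4g. The longest span is 78 − 12 = 66 weeks (1.5-year study, 12-week participation).

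| Span S (weeks) | Gap g | Fifth scan at 4g | Started, for L = 1, 2, 3, 4 |
|---|---|---|---|
| 2 | 0.22 | 0.9 | 0, 0, 0, 0 |
| 9 | 1.00 | 4.0 | 3, 2, 1, 0 |
| 13 | 1.44 | 5.8 | 4, 3, 2, 2 |
| 26 | 2.89 | 11.6 | 4, 4, 3, 3 |
| 66 | 7.33 | 29.3 | 4, 4, 4, 4 |

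The count is zero only if 4g ≤ L, that is, if the first five scans fall within 1 to 4 weeks of each other. These are best cases, with the first five matrices all anomalous.

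**A later trigger.** Let p be the share of patients anomalous in one given area (not in the documents; patients taken as independent). The chance that the area reaches 5 of 10, and the mean number of patients scanned before the trigger when it does, are:
- p = 0.3: 15.0%, 7.7
- p = 0.5: 62.3%, 7.0
- p = 0.7: 95.3%, 5.9
- p = 0.9: about 100%, 4.6

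The number scanned is an upper limit on the number started.

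**The sections side by side.** Take a patient whose two highest-count extra sites do not include the shared area. Under 6.1.2 that patient receives those two sites. Under 9.1.1 the third treatment goes to the shared area. Nothing in either section says which prevails.

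**The case against.** *The timing may be set elsewhere.* Figure 1 is not shown, Section 8.1 defers to it for the schedule, and 6.1.2 leaves operating details to an on-site SOP or user guide. A reader might infer that the plan contains no hold at all. The documents do not support that; only the supplied text can be said to lack one.

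*The harm depends on accrual.* Recruitment is from one clinic with a prepared patient list (5.5), so clustered baselines are possible, and the table shows zero patients started in that case. This stands. The same section expects to screen 40 people, and nothing promises that scans will be clustered.

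*Treated early does not mean unstimulated.* A reader might infer that four or more patients would miss the shared area. The counts do not show that. In the best case every pre-trigger patient is anomalous in that area and may have received it as an own site. The number unstimulated cannot be derived and could be zero.

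*The test may already be restricted.* Section 9.1.1 links the test to targeting the area in everyone and never says to pool unstimulated patients. That is fair: mixing is a possibility the text leaves open, not an instruction.

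*The threshold and the ranking do not conflict.* Four or more anomalies defines candidates, and the highest count ranks them. The two are compatible, and a synopsis need not repeat the threshold. Likewise, the natural reading of the third treatment is that the lower-ranked extra site gives way. What remains is that 1.1 and 6.1.2 do not mention the shared area.

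*Half might be read as a running share.* With the sample fixed at 10, 5 of 10 is the plain meaning, and nothing here rests on another reading.

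**Conclusion.** The point holds in limited form. As supplied, the text cannot assign the shared area to all patients unless five anomalous matrices for it are in hand before the first treatment. Otherwise some patients will have started on targets from their own matrix: up to 4 if the first five scans are all anomalous, more with a later trigger. How many of these would go unstimulated at the shared area is unknown. Sections 6.1.2 and 9.1.1 can also give one patient different third targets, whatever the accrual pattern.

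The reach is one target slot in exploratory aim 3. A reader might infer that the primary analysis is weakened or that a common target is a mistake. Neither follows: right TGd goes to every patient, its test and power do not depend on this rule, and a common target is a legitimate choice. If no area reaches 5 of 10, the descriptive fallback applies and only the mismatch between sections remains. This is a minor point, held with medium confidence because accrual is unstated and Figure 1 and the SOP are unseen.

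**What to change.** Keep the shared target and add a short clause to 9.1.1, with a cross-reference in 6.1.2:

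1. The shared area applies only to patients not yet treated when the fifth anomalous matrix for that area is seen.
2. It replaces the extra site with fewer anomalies.
3. A patient who already has it as an own site keeps both own sites.
4. The common-target t-test includes only patients stimulated at that area; the others are reported separately.

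The cost is one paragraph and one cross-reference, with no added visits, scans or patients. The downside is that the common-target test may cover fewer than 10 patients. Holding treatment until enough scans are in would also settle the timing, but it would change the windows in 1.3 and 8.1.3. With even entry over 66 weeks, the first patient would wait at least 29.3 weeks for the fifth scan, against a stated participation of 10 to 12 weeks.
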